ovocation test (0-10 NPRS) nsion test (0-10 NPRS) old at the tibial tubcle (kPa) ee extenstion strength (Nm/kg) np height (cm) s of sports participation s of physical activity anual palpation ovement jump (0-10 NPRS)
nsion test (0-10 NPRS) id at the tibial tubcle (kPa) ee extenstion strength (Nm/kg) np height (cm) s of sports participation s of physical activity anual palpation ovement jump (0-10 NPRS)
and at the tibial tubcle (kPa) ee extension strength (Nm/kg) np height (cm) s of sports participation s of physical activity anual palpation ovement jump (0-10 NPRS)
ee extenstion strength (Nm/kg) np height (cm) s of sports participation s of physical activity anual palpation ovement jump (0-10 NPRS)
np height (cm) s of sports participation s of physical activity anual palpation ovement jump (0-10 NPRS)
s of sports participation s of physical activity anual palpation ovement jump (0-10 NPRS)
s of physical activity anual palpation ovement jump (0-10 NPRS)
anual palpation ovement jump (0-10 NPRS)
ovement jump (0-10 NPRS)
ver (W)
ty change (°)
kening or hyperemia)
I tubercle ad modum Ohberg
gns (thickening or hyperemia)
erity score
or moderating the effect on selected outcomes
ffset
erity score
e apophysis
S-child child question P1 on 'Pain' subscale (1-5 likert scale)
a Scale of Kinesiophobia, 17 items)
(0-10 NPRS)
or mediating the effect on the primary outcome
past week (0-10 NPRS) at week 4
ain threshold at the tibial tubcle (kPa) at week 4
oort (<2 hours/week) at week 5
no.) at week 13
WAI) at week 13
bia (Tampa Scale of Kinesiophobia, 17 items) at week 13
bia (Tampa Scale of Kinesiophobia, 17 items) at week 13 knee extension test (0-10 NPRS) at week 13
knee extension test (0-10 NPRS) at week 13
knee extension test (0-10 NPRS) at week 13 ometric knee extenstion strength (Nm/kg) at week 13
knee extension test (0-10 NPRS) at week 13 ometric knee extenstion strength (Nm/kg) at week 13 la tendon hyperemia (ad modum Öhberg 1-4) at week 13
knee extension test (0-10 NPRS) at week 13 ometric knee extenstion strength (Nm/kg) at week 13 la tendon hyperemia (ad modum Öhberg 1-4) at week 13
knee extension test (0-10 NPRS) at week 13 ometric knee extenstion strength (Nm/kg) at week 13 la tendon hyperemia (ad modum Öhberg 1-4) at week 13 r bursitis signs (thickening or hyperemia) at week 13

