## Statistical methods

## Statistical methods for primary and secondary outcomes (20a)

Analyses will be performed by a statistician blinded to group allocation and will be performed using (R Foundation for Statistical Computing, Vienna, Austria) in the Rstudio interface (RStudio Team, Boston, USA).

Change scores for KOOS-child 'sport/play' score ( $\triangle$ KOOS) from baseline to month 5 will be calculated for all participants. We will fit a linear regression model using the 'lm' function for  $\triangle$ KOOS-child as the dependent variable and including group allocation as an independent variable. Covariates are described with their measurement, timing and justification in table 12, and will potentially be added to the model.82(p9),215 In order to not introduce unnecessary bias in the model, covariates will however only be included if doing so changes the primary estimate meaningfully, as we expect a equal distribution of these pre-specified covariates given the sample size. Significance level will not determine the inclusion of covariates. The linear model will be evaluated for linearity, multicollinearity, homogeneity of variance, distortion of outliers, homoskedasticity, correlation of variables, distribution of residuals using histograms. If these model assumptions are not met non parametric bootstrap estimation and tests will be used instead. Below we have outlined the intended steps with reproducible R code for Rstudio (version 3.6, 2021.09.0+351)

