## Assumptions for causal mediation analysis

The four assumptions for unconfounded analysis of parsed mediation pathways require 1) no unmeasured exposure-outcome confounders, 2) no unmeasured mediator-outcome confounders, 3) no unmeasured exposure-mediator confounders, 4) no mediator-outcome confounder affected by exposure. Assumption 1 and 3 should be mitigated by randomization and potential covariate adjustment. Because mediators are not randomized it is possible for the mediator-outcome pathway to be confounded (assumption 2 and 4). To address assumption 2, we will include pre-treatment confounders based on available evidence and clinical expertise. This includes potential covariates/moderator variables outline (table 12) and baseline levels of the mediator-variables. Assumption 4 will be addressed by using interventional effects in the mediation analysis along with inclusion of confounders. In addition, to address the assumption of no positivity, that is, a zero risk of any participant exhibiting a positive characteristic of a mediation variable at baseline, all mediator variables with this potential issue, will be change-scores calculated from baseline.

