## Number of predictors for mediations analysis

Based on our sample size of n=130 and the use of multiple regression models, power of >80% and alpha level of 5% (t = 1.658, Df = 109), we calculated the potential number of predictors as 16 based on Fritz & MacKinnon sample size recommendations for mediation analysis (G\*power 3.1.9.7, Düsseldorf University, Germany). In our current model, we have included 15 predictors (8 mediators and 7 potential covariates/moderators).

Variables	Measurement	Justification
Potential moderators/c	ovariates	
Growth velocity w0	Offset from predicted age at peak height velocity in years, calculated from clinically measured anthropometrics: sitting height, bodyweight, total stature, biological age.  Participants will be categorized into pre- (<-1.0 years offset), circa- (-1.0 to +0.5 years offset), and post-PHV (>+0.5 years offset), corrected for timing of the primary endpoint, resulting in a 5 month subtraction.	Overuse knee injuries, as well as injuries to the growth plate, in sports active adolescents are higher during peak height velocity and the year leading up to this point,  which is thought to be primarily due to vulnerable growth-related conditions, such as Osgood-Schlatter.  This has been supported by data showing higher growth velocity for Osgood-Schlatter patients than controls. 
Growth timing w0	Based on algorithms for calculating anticipated age of peak height velocity which incorporates data on parents adult stature, we will classify participants as early maturers, average maturers, and late maturers (girls: <10.94, 10.94-12.94, and >12.94 years, respectively; boys: <12.64, 12.64-14.64, and >14.64 years, respectively). 	Reaching skeletal maturity either late or on average is a risk factor for developing Osgood-Schlatter compared to early maturation. 
Fear of movement w13	Fear of movement will be captured by participants filling in the 17 items Tampa Scale of Kinesiophobia, each item scored on a 4-point likert scale with a score ranging from 0 to 68. 	Avoidance behavior might be related to a too apprehensive approach to gradual exposure and exercise therapy resulting in the patient not achieving a higher degree of participation in sports and physical activity. Osgood-Schlatter patients exhibits a high degree of kinesiophobia. 

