Pressure sensitivity w4	Through handheld algometry, the patient denotes when pressure applied to the symptomatic tibial tubercle goes from feeling as "pressure" to "pain", and the kPa at this threshold is recorded. Change score is calculated from baseline.	The aim of the sports break is to calm the sensitivity of the condition to achieve a more successful graded exposure to sports and physical activity.  Besides pain intensity, one way to measure decreased sensitivity of the condition is through pressure-pain detection threshold to evaluate local hyperalgesia specifically at the tibial tubercle.					
Controlled return to sport w5	Sports participation in the preceding week is self- reported through weekly text messages, ranging from 0 to >7 hours. <2 hours of sports participation in week 5 will be considered as a controlled return to sport.	Graded exposure requires a gradual introduction to sports, although this trajectory quickly can be accelerated if it appears to be tolerated. In the very first week of a gradual return to sports, modest sports participation should be a marker of adhering to the recommendation of gradual return.					
Pain flare frequency during return to sport w13	Number of pain flares (episodes of NRPS ≥4) in the preceding week is self-reported through weekly text messages.	Graded exposure according to the pain-model aims to both prevent pain flares, and to mitigate their intensity to NRPS ≤3.					
Therapeutic Alliance w13	Therapeutic Alliance will be captured by participants filling in the 12 item short-form Working Alliance Inventory, each item scored on a 7-point likert scale with a score ranging from 0 to 84 points. 	Achieving a strong therapeutic alliance has been shown to be related to improved outcomes in trials across several musculoskeletal conditions. 					
Fear of movement w13	Fear of movement will be captured by participants filling in the 17 items Tampa Scale of Kinesiophobia, each item scored on a 4-point likert scale with a score ranging from 17 to 68. 	Avoidance behavior might be related to a too apprehensive approach to gradual exposure and exercise therapy resulting in the patient not achieving a higher degree of participation in sports and physical activity. Osgood-Schlatter patients exhibits a high degree of kinesiophobia. 					

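### Table 12 dates the candidate covariate fear of movement at week 13, very probably a slip for week 0, so the primary model could adjust for a mediator

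*Combined protocol and SAP*

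**What the plan says.** The section on statistical methods for primary and secondary outcomes fits a linear regression of the change in KOOS-child Sport/play on group. On adjustment it says: "Covariates are described with their measurement, timing and justification in table 12, and will potentially be added to the model". The inclusion rule is that "covariates will however only be included if doing so changes the primary estimate meaningfully". No cut-off is given. The reason offered is that the covariates are expected to be balanced between arms.

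Table 12 prints fear of movement twice, both times with the subscript w13:

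- In the block of potential moderators/covariates: "each item scored on a 4-point likert scale with a score ranging from 0 to 68". The other seven rows of this block carry w0.
- In the block of potential mediators: "each item scored on a 4-point likert scale with a score ranging from 17 to 68".

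Table 1 also has the Tampa scale in both roles. The moderator entry has no week; the mediator entry reads "Tampa Scale of Kinesiophobia, 17 items) at week 13".

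The section on assumptions for causal mediation analysis treats the covariates as baseline variables: "we will include pre-treatment confounders based on available evidence and clinical expertise. This includes potential covariates/moderator variables outline (table 12"), together with "baseline levels of the mediator-variables". Table 11 schedules the Tampa scale at months 0, 3 and 5.

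**The concern.** A week-13 score is measured when the supervised treatment ends. The plan's own section on effect moderation and mediation defines a mediator as a post-randomisation variable that treatment is thought to influence, and this score is on its list. Conditioning on it in the primary model removes whatever part of the treatment effect runs through fear of movement. The result is no longer the total effect of offering the new treatment rather than usual care, which is what the intention-to-treat analysis is meant to estimate.

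The inclusion rule makes the label matter more. A rule that keeps covariates because they shift the treatment estimate tends to pick variables that differ between arms, and a treatment-affected variable is the likeliest of these. The only time-order rule, under the statistical approach to mediation analysis, applies to mediators and not to covariates. That section also puts the covariates into the full mediation model, so one week-13 variable would be both covariate and mediator there.

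**Working it through.** **1. Which week was meant?** Five things in the documents point to week 0:

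- the other seven covariate rows are w0;
- the mediation assumptions call the Table 12 covariates pre-treatment;
- the expectation of balance between arms is one that randomisation supports only for baseline values;
- Table 1 attaches week 13 to the mediator entry only;
- a month-0 Tampa score is scheduled.

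Nothing in the plan argues for a week-13 covariate.

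**2. The plan's own figure.** Inputs from the sample size section: difference 9, SD 16, one-sided 5%, power 90%. The one-sided two-sample t-test needs 54.82 per group, matching the stated 54.8 (55). Dropout: 110 / 0.85 = 129.4, so 130. Power at 55 per arm is 90.1%. The sample size is not in dispute and is the base case below.

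**3. Effect of using the week-13 score.** Let d be the between-arm difference in week-13 fear in SD units (positive if fear is lower in the experimental arm) and r the size of its within-arm correlation with the outcome. The documents give neither, so both are assumed. If the covariate is always included:

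- adjusted effect = 9 − 16 × r × d
- standard error = 16 × √(1 − r²) × √(2/55) × √(1 + d²/4)

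For d = 0.3 and r = 0.5, the effect is 9 − 16 × 0.5 × 0.3 = 6.6. The standard error is 16 × 0.866 × 0.1907 × 1.011 = 2.67, and power from the noncentral t is 79%. A 5,000-trial simulation of this case gave 6.6 points and 79%, with the unadjusted estimate at 9.0.

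**4. Adding the inclusion rule.** The plan gives no value for a meaningful change, so cut-offs of 10% and 20% of the unadjusted estimate are assumed. The covariate is kept if |adjusted − unadjusted| is at least the cut-off times |unadjusted|. Simulation used 200,000 trials per setting, 55 per arm and a true effect of 9. Cells show mean final estimate / power:

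| Shift d | r | 10% cut-off | 20% cut-off |
|---|---|---|---|
| 0 | 0.3 | 9.02 / 91.7% | 9.07 / 91.3% |
| 0 | 0.5 | 9.02 / 95.0% | 9.15 / 94.3% |
| 0.1 | 0.3 | 8.65 / 89.0% | 8.86 / 89.1% |
| 0.1 | 0.5 | 8.26 / 91.4% | 8.56 / 90.8% |
| 0.3 | 0.3 | 7.70 / 81.4% | 8.18 / 82.4% |
| 0.3 | 0.5 | 6.63 / 78.2% | 6.91 / 78.1% |
| 0.5 | 0.3 | 6.65 / 70.1% | 7.05 / 71.0% |
| 0.5 | 0.5 | 5.00 / 56.6% | 5.07 / 56.8% |
| −0.3 | 0.3 | 10.30 | 9.89 |
| −0.3 | 0.5 | 11.32 | 11.05 |
| −0.5 | 0.3 | 11.33 | 10.92 |
| −0.5 | 0.5 | 12.97 | 12.78 |

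- Loss at d = 0.1: from 9 − 8.86 = 0.14 to 9 − 8.26 = 0.74 points.
- Loss at d = 0.3 to 0.5: from 9 − 8.18 = 0.82 to 9 − 5.00 = 4.00 points.
- Inflation at d = −0.3 to −0.5: from 9.89 − 9 = 0.89 to 12.97 − 9 = 3.97 points.

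How often the covariate enters varies. At the 10% cut-off with r = 0.5 it entered in 88% of trials at d = 0.3, and at d = r = 0.5 in 99%. At d = 0.3, r = 0.3 and a 20% cut-off it entered in 35%.

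**5. With the covariate dated week 0.** The expected d is 0, so the adjusted estimate targets the full 9 points. If it is always included, power at 55 per arm is about 92% (r = 0.3) to 96% (r = 0.5).

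**The case against.** The strongest reply is that this is a typing slip costed as though it were a design choice. A sensible analyst would read week 0, and nothing would be lost. Harm to the primary result needs four things together: the label taken literally, adjustment allowed in the primary model, a real between-arm difference in week-13 fear, and a shift that passes an undefined threshold. The section on additional analyses lists covariate adjustment among the sensitivity analyses, and the example code adjusts for maturation timing, not fear. The power figures rest on assumptions that do not fix even the direction.

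Most of this stands. It is why the point is minor and why the figures are illustrations. It does not settle the matter, because the primary methods section names Table 12 as the source of covariate timing, and the statements pointing to baseline values are written mainly for the mediation analysis. The sections also disagree on whether the primary estimate is adjusted: the example model does include a Table 12 covariate.

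A second reply is that the row may be a stray copy of the mediator row, to be deleted and not re-dated. The text before Table 12 counts 7 covariates, which equals the number of w0 rows, and the two fear-of-movement rows share their justification. Against this, the mediator count is also off (8 stated, 10 printed), Table 1 keeps the Tampa scale among the moderators, and baseline levels of the mediators are already planned as confounders. On either reading the printed row is wrong, and a week-0 covariate avoids the bias.

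**Conclusion.** The concern holds, at minor severity. That the covariate label conflicts with the rest of the plan is near certain; that week 0 was intended is a well-supported inference. The effect on the primary result is conditional. It is nil if the label is read as week 0, if the arms do not differ on week-13 fear, or if adjustment is confined to sensitivity analyses. In that last case the label, read literally, still affects the covariate-adjusted sensitivity analysis and leaves one variable in two roles in the mediation model. If the plan is followed literally in the primary model, a between-arm difference of 0.3–0.5 SD moves a 9-point effect by roughly 1 to 4 points in either direction, and power falls to between 82% and 57% when the difference favours the experimental arm. These figures assume a correlation of 0.3–0.5 and a cut-off of 10% or 20%; the documents supply neither, nor the between-arm difference.

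**What to change.** Before unblinding:

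1. Change the subscript of fear of movement in the covariate block of Table 12 from w13 to w0.
2. State that only variables measured before randomisation may enter the primary model.
3. Keep the week-13 Tampa score as a mediator only.
4. State whether the primary estimate is unadjusted, as the section on additional analyses implies, or may include baseline covariates, as the primary methods section and example code imply.

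The cost is one subscript and two sentences. No new data are needed, since the baseline Tampa score is already in the schedule, and the sample size does not change. The differing score ranges in the two fear-of-movement rows and the predictor counts can be tidied in the same edit, but nothing here depends on them.

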#### Statistical code example

#### Step 1: load necessary packages

#installs and loads all necessary packages

install.packages("stargazer")
library("stargazer")
install.packages("ggplot2")
library("ggplot2")
install.packages("performance")
library("performance")
install.packages("lindia")
library("lindia")
install.packages("see")
library("see")
install.packages("patchwork")
library("patchwork")
install.packages("readr")

library(readr)

#### Step 2: import data

```
#imports csv file into dataframe titled fu_data
fu_data <- read_delim("R/win-library/3.6/fu_data.csv", ";", escape_double = FALSE, trim_ws = TRUE)</pre>
```

#### Step 3: run regression model

[figure not shown]
```
#runs linear regression model with `koos_spor't as the dependent outcome variable
#and `group' as the independent predictor variable. The model is named lm_koos_sp
#`timing' of maturation is included as a covariate.
```

```
lm_koos_sp <- lm(koos_sport~group + timing, data=fu_data)</pre>
```

#### Step 4: produce plots for model evaluation

```
#produce plots used for evaluation of model fit and assumptions
```

gg\_diagnose(lm\_koos\_sp)
check\_model(lm\_koos\_sp)

## Step 5: evaluate model from plots

#### Step 6: print model output

```
#prints output from model from summary and stargazer function
summary(lm_koos_sp)
stargazer(lm_koos_sp, type = "text", style="all", title="Linear regression of KOOS-child
sport/rec")
```

#### Step 6: evaluate model output from console

```
Residuals:
  Min 1Q Median 3Q Max
-4504.4 -2863.1 485.1 2421.4 4720.6
Coefficients:
        Estimate Std. Error t value Pr(>|t|)
(Intercept) 4541.2 2215.4 2.050 0.0498 *
         1050.6
                  1145.6 0.917 0.3670
group
         -1056.5
                   776.5 -1.360 0.1845
timing
___
Signif. codes: 0 `***' 0.001 `**' 0.01 `*' 0.05 `.' 0.1 ` ' 1
Residual standard error: 3105 on 28 degrees of freedom
 (2 observations deleted due to missingness)
Multiple R-squared: 0.07503, Adjusted R-squared: 0.008959
F-statistic: 1.136 on 2 and 28 DF, p-value: 0.3356
Linear regression of KOOS-child sport/rec
Dependent variable:
               _____
                      koos_sport
_____
                       1,050.577
group
                      (1, 145.632)
                      t = 0.917
                       p = 0.367
timing
                       -1,056.458
                       (776.549)
                       t = -1.360
                       p = 0.185
                      4,541.163**
Constant
                       (2, 215.364)
                       t = 2.050
                       p = 0.050
-----
Observations
                          31
                        0.075
R2
Adjusted R2
                        0.009
Residual Std. Error 3,104.971 (df = 28)
```

F Statistic	1.136 (df = 2; 28) (p = 0.336)
Note:	*p<0.1; **p<0.05; ***p<0.01

We expect only to modify these procedures if more suitable methods, packages, or software is developed and will describe and justify these potential deviations from the pre-specified strategy in the final report. Intention-to-treat analyses, that is, analysis according to group allocation, will be performed as the standard analysis strategy unless otherwise denoted, to 1) investigate the relative effectiveness of being offered the experimental intervention over usual care, and 2) to maintain the balance of known and unknown confounders from randomization.

We will employ a similar analysis strategy for other numerical outcome variables. For non-numeric variables, differences between groups will be analyzed by logistic regression models, and non-normally distributed residuals for ratio-interval scale outcomes will be compared by non parametric boot strap tests. To supply detailed trajectories and inferences of treatment response over time, we will fit mixed-effects models for the imaging outcomes (months 0, 3, 5, 8); time-to-return to sport, weekly hours of sports participation, pain-flares, and sensor-based physical activity (weeks 0 to 22); clinical outcomes (months 0, 1, 3, 5, 8); and remaining patient-reported outcomes (months 0, 1, 3, 5, 8, 12, 24, 48).

Mean and SD values will be reported if data appear approximately normally distributed. If data are nonnormally distributed, they will be presented as median and interquartile range (IQR). We will report 95% confidence intervals, exact p-values to the third decimal, and discussions of minimal detectable change (MDC) and minimal important change (MIC) when relevant/possible. Frequency data will be reported as "No. (%)".

Our standard option for all variables, is to be analyzed with the highest resolution possible, meaning no collapsing or dichotomization to retain as much information as possible in the dataset. However, some assessor-dependent scales, such as ultrasound scoring of the (non-normal maturation-related) fragmentation quality of the tibial tubercle bone, contains the potential values "none" (1), "unclear", (2), "little", or "apparent/extensive" (4). The same applies to some other ultrasound measures and clinical examination findings. Depending on the distribution of responses into these categories, we might choose to exclude data from the "unclear" category or collapse the "little" and "apparent/extensive" categories if we estimate the number of responses to be too low to make meaningful inferences.

Once the primary data have been analyzed, we will also compute and report the RCT-Fragility Index (how

many patients would need to change from success to non-success to render the potential experimental effect non-significant or equal) based on the PASS outcome for easier clinical interpretation of the robustness of results.

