## Handling of non-adherence and any statistical methods to handle missing data {20c}

Assuming that data will be missing at random, multiple imputations using chain equations will be used to handle missing data. Imputation models for missing variables will be fitted using linear, logistic or polytomous regression models. All available variables will be included in the imputation models, unless a specific reason is given for exclusion. Imputation will only be performed for variables included in the

[figure not shown]
analysis. Multiple imputation will be done using R-package mice[].

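### The R code given as the intended primary analysis drops incomplete cases and always adjusts for maturation timing, which conflicts with the SAP text on imputation and covariates

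*Combined protocol and SAP*

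**What the plan says.** **Text.** In *Statistical methods for primary and secondary outcomes*, the primary model is a linear regression of the change in KOOS-child Sport/play from baseline to month 5 on group. The covariates in Table 12 are candidates that will "only be included if doing so changes the primary estimate meaningfully". *Methods for additional analyses* lists the covariate-adjusted model among the sensitivity analyses. In *Handling of non-adherence and any statistical methods to handle missing data*, "multiple imputations using chain equations will be used to handle missing data", with the R package mice.

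**Code.** The block is headed as an example, but the text introduces it with "Below we have outlined the intended steps with reproducible R code for Rstudio". After the printout the SAP adds: "We expect only to modify these procedures if more suitable methods, packages, or software is developed", and promises to describe and justify any deviation.

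- Step 1 says it loads every package needed and names seven: stargazer, ggplot2, performance, lindia, see, patchwork and readr. mice is not among them.
- Step 2 imports a prepared CSV file.
- Step 3 fits "lm_koos_sp <- lm(koos_sport~group + timing, data=fu_data", and its comment says that timing "of maturation is included as a covariate".
- The later steps check and print that one model. The printout includes "2 observations deleted due to missingness".

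**The concern.** A SAP should lead any competent analyst to the same primary estimate. Here an analyst who runs the printed steps obtains a complete-case estimate adjusted for timing. One who follows the prose obtains a multiply imputed estimate, unadjusted unless some covariate is judged to move it. Either could be called pre-specified.

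Two things are at stake. Participants with incomplete rows leave the analysis under one reading and stay under the other, which matters if those lost differ in ways the imputation model could capture. The analyst also has room to choose, and the text sets no threshold for how far the estimate must move before a covariate enters. The trial plans to share the code for its primary outcome with the main publication, so a mismatch with this plan would be visible.

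**Working it through.** **1. The plan's own figure.** From *Sample size considerations*: difference δ = 9, SD = 16, one-sided α = 0.05, power 90%, dropout 15%.

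Power = P(T > t(0.95; 2n − 2)), where T is noncentral t with 2n − 2 degrees of freedom and noncentrality (9/16)·√(n/2). Solving for 90% gives n = 54.82 per group (plan: 54.8, rounded to 55). Then 110 / 0.85 = 129.4, rounded up to 130. The sample size reproduces. With 65 per group, power is 93.9%, against the plan's 94.6%; the gap has no bearing here.

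**2. Text and code side by side.**

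| Element | Text | Code |
|---|---|---|
| Missing data | Chained-equation imputation with mice | No imputation or pooling; mice not loaded; `lm` by default drops any row with a missing value |
| Covariates | Conditional on a meaningful shift in the estimate; adjustment also called a sensitivity analysis | Timing in the only model fitted; no unadjusted fit, no comparison |
| Outcome | Change from baseline to month 5 | `koos_sport`, an imported column, never derived or defined |
| Test | One-sided | Printed p-value is two-sided |
| Interval | 95% confidence interval | Standard error only |

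The first two rows cannot both be followed. The third can be reconciled if the imported column already holds the change. The last two are omissions from the example.

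**3. What the printout shows.** Rows: 31 used + 2 deleted = 33, so 2/33 = 6.1% were dropped. Parameters: 31 − 28 residual df = 3, namely intercept, group and one slope for timing. If this is the growth timing of Table 12, which has three classes, a categorical term would need two coefficients. For group, t = 1,050.577 / 1,145.632 = 0.917, giving two-sided p = 0.367 and one-sided p = 0.183. A residual standard error of 3,105 is impossible for a 0-100 score or its change, so these are placeholder data. The printout shows how the code behaves and says nothing about the trial's data.

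**4. Size, if dropout becomes missing month-5 data.** At 15%: 0.15 × 130 = 19.5, about 20 participants. At the pilot's 20% (3 of 15): 0.20 × 130 = 26. Complete-case power at δ = 9 and SD = 16, one-sided 0.05:

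| Missing | Complete cases | Power |
|---|---|---|
| 0% | 130 | 93.9% |
| 5% | 123.5 | 92.8% |
| 10% | 117 | 91.6% |
| 15% | 110.5 | 90.2% |
| 20% | 104 | 88.6% |

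The code also drops anyone with a month-5 score but no timing value. Table 12's growth timing needs the parents' adult stature, so such gaps are possible; their number cannot be predicted from the documents.

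**5. Does the outcome's definition matter?** Write Y5 and Y0 for the month-5 and baseline scores and G for group. If the model is Y5 = a + bG + cY0 + e, subtracting Y0 from both sides gives Y5 − Y0 = a + bG + (c − 1)Y0 + e. The group effect b and the residuals are unchanged. Without Y0 in the model, the month-5 and change analyses differ by the chance imbalance in baseline, so the definition then matters.

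**The case against.** The block is titled an example and runs on dummy rows. The prose rule on missing data is explicit, and no passage proposes a complete-case primary analysis. The text says covariates may be added, so the code may simply illustrate an adjusted fit. The statistician is blinded and deviations must be justified. All of this is fair and keeps the point modest. It does not remove it, because the same section calls the steps intended and expects to depart from them only for better tools.

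Four stronger readings are tempting, and the documents do not support them:

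- *The code contradicts the change-score analysis.* `koos_sport` is undefined and may hold a change computed before import.
- *Text and code give different results.* They can; nothing shows that they will. If only the outcome is missing and the imputation uses the same predictors as the model, the two estimates nearly coincide under missing at random. Divergence would come through the auxiliary variables that the SAP plans to use, or through missing timing values.
- *The code breaches intention-to-treat.* The SAP defines that term as analysis by allocated group and handles missing data separately.
- *The trial would be under-powered.* The sample size already allows for 15% loss.

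It is also fair that 15% is a planning allowance. The retention plan, with reminders, telephone calls and electronic-only completion, may leave fewer month-5 scores missing.

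**Conclusion.** The point stands in limited form. Code and text specify different primary analyses on missing data and on covariates, and the outcome variable in the code is undefined. Up to about 20 of 130 participants would be treated differently, on the assumption that the full 15% allowance turns into missing month-5 outcomes; with better retention the number is smaller. Power at that loss is about 90%, so the consequence is possible bias and freedom to choose between specifications. No sample-size figure changes. It should be corrected, because the inconsistency concerns the primary estimate and is cheap to remove.

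**What to change.** Before allocation is unblinded, replace the example with code for one primary analysis:

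1. Derive and name the outcome from the baseline and month-5 Sport/play scores.
2. Impute with mice, using the variables the missing-data section describes.
3. Fit one fixed model in each imputed set and pool, for example `with(imp, lm(sport_m5 ~ group + sport_m0))` followed by `pool()`.
4. Report the pooled difference, its confidence interval and the one-sided p-value in the pre-specified direction.

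Drop both the data-driven covariate rule and the unconditional timing term from the primary model. Label the complete-case and timing-adjusted fits as sensitivity analyses.

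Baseline Sport/play in the sketch is a separate improvement and goes beyond aligning the code with the present text. The score is already collected, it can only be expected to help precision, and by step 5 of the working it makes the month-5 and change analyses give the same group effect. If it is adopted, amend the paragraph on the primary model so that text and code agree. If not, the minimum repair is the change score on group alone, imputed and pooled.

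The cost is about ten lines of code and a short text amendment. No new data are needed.
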